## 7.1.2.13.2.1 Reporting Events of Hypoglycemia

All episodes considered as likely to represent symptomatic hypoglycemia by the investigator must be captured as an adverse event of "symptomatic hypoglycemia." This diagnosis may be supported by, *but does not require*, confirmatory blood glucose results (such as those measured using a fingerstick or from a clinical laboratory sample). Further, at the discretion of the investigator, an asymptomatic blood glucose value ≤70 mg/dL (3.9 mmol/L) may be reported as an adverse event of "asymptomatic hypoglycemia." General guidance regarding the determination as to whether an event is considered to be an adverse event should be followed (see Section 7.2).

Regardless of whether an episode is considered an adverse event, the HA eCRF *must* be completed for the following:

- all episodes determined by the investigator to be hypoglycemia (symptomatic or asymptomatic).
- all glucose values ≤70 mg/dL (3.9 mmol/L).

# 7.1.2.13.3 Urinary Tract Infections

Any subject presenting with symptoms considered to be a urinary tract infection should be recorded as having an adverse event with the term as considered appropriate by the investigator (e.g., cystitis, pyelonephritis, urinary tract infection). The site should collect urine for culture performed by their local laboratory, but urine dipstick should not be performed by the site or local laboratory. If a urinalysis is clinically necessary, a microscopic urinalysis ONLY and not a dipstick urinalysis should be performed. If symptoms are reported outside of a routine scheduled study visit, clinical assessment and urine testing should be done promptly at an unscheduled visit. The investigator or treating physician should initiate antibiotic treatment as considered clinically appropriate; if possible, a locally obtained culture and sensitivity should be obtained. The choice of antibiotic agent and duration of treatment is left to the investigator's or treating physician's discretion.

Additionally, if a subject reports a urinary tract infection treated by another physician, this episode will be captured as an adverse event. The site should attempt to obtain information from the treating physician regarding diagnostic tests performed (excluding urine dipstick results) and treatment provided, and this information should be recorded.

**Protocol/Amendment No.:** 002-01

#### 7.1.2.13.4 Genital Fungal Infections

Subjects who suspect that they have a genital fungal infection should be encouraged to report this to investigators. The investigator or treating physician can initiate antifungal treatment either empirically as per local practice or following results from genital swab collected and analyzed by the central laboratory. The choice and duration of antifungal agent used is left to the investigator or treating physician's discretion.

# 7.1.3 Laboratory Procedures/Assessments

All laboratory tests outlined in the Trial Flow Chart - Section 6.0 will be performed by the central laboratory. The fasting fingerstick glucose measurements, optional site fingerstick A1C at Visit 1/Screening, and all urine pregnancy tests will be performed at the investigational site.

Laboratory test results for chemistry, hematology, urinalysis (except urine glucose), and lipids will not be masked. Glycemic measurements (e.g., FPG, A1C) and C-peptide measurements will be masked from Visit 4/Randomization (Day 1). However, in order for the investigator to perform an evaluation for possible rescue or discontinuation from the blinded investigational product, the central laboratory will report to the investigator in an unmasked manner if an FPG or A1C value meets criteria for glycemic rescue or discontinuation from blinded investigational product criteria (see Sections 5.6 and 5.8).

In addition, the central laboratory will flag the following safety measurements meeting specific criteria for discontinuation from blinded investigational product:

serum creatinine  $\geq 1.5 \text{ mg/dL}$  (133 µmol/L) in men or  $\geq 1.4 \text{ mg/dL}$  (124 µmol/L) in women;

eGFR <45 mL/min/1.73 m^2;

elevations  $\ge 3X$  ULN in liver transaminases (i.e., ALT and AST) (see Section 12.5 for guidance on retesting);

elevations in ALT and/or AST  $\geq$ 3-times the ULN with concurrent total bilirubin  $\geq$ 2-times the ULN and alkaline phosphatase  $\leq$ 2-times the ULN;

positive serum pregnancy test

Laboratory safety tests will be performed after at least a 10-hour fast. All laboratory measurements must be performed by the central laboratory.

Details regarding specific laboratory procedures/assessments to be performed in this trial are provided below.

Refer to the Trial Flow Chart - Section 6.0 for specific laboratory tests performed at each trial visit.

MK-8835-002-01 Final Protocol

26-Feb-2015

**Protocol/Amendment No.:** 002-01

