- FPG consistently >240 mg/dL (13.3 mmol/L) after Visit 5/Week 6 through Visit 6/Week 12.
- FPG consistently >200 mg/dL (11.1 mmol/L) after Visit 6/Week 12 through Visit 8/Week 26.
- FPG consistently >200 mg/dL (11.1 mmol/L) or A1C >8.0% (64 mmol/mol) after Visit 8/Week 26

Phase B/Year 2: Subjects who have a repeated, confirmed FPG >200 mg/dL (11.1 mmol/L) or single A1C >8.0% without a reasonable explanation (e.g., intercurrent illness or medication omission) despite receiving a maximum labeled or maximum tolerated (if lower than maximum labeled) dose of glimepiride/matching placebo for at least two weeks.

**Note:** A consistent value for FPG is defined as a repeat measurement performed within 7 days of notification from the central laboratory. Site should reinforce diet/exercise counseling prior to repeat measurement.

- 3. Hypoglycemia: Repeated (2 or more episodes since the prior visit) FPG or fingerstick glucose
  - <50 mg/dL (2.8 mmol/L) with or without symptoms of hypoglycemia, or
  - ≤70 mg/dL (3.9 mmol/L) with symptoms of hypoglycemia, and without a reasonable explanation (e.g., increased physical activity or skipped meal) or with a reasonable explanation and likely to reoccur.

**Note:** Subjects should only be discontinued from blinded investigational product due to hypoglycemia after the subject has down-titrated and interrupted glimepiride/matching placebo (see Section 5.2.1.2.2). Subjects rescued with sitagliptin must first interrupt sitagliptin and if the subject continues to experience hypoglycemia, the dose of glimepiride/matching placebo should be down-titrated and if necessary interrupted. If the subject continues to experience hypoglycemia despite interruption of glimepiride/matching placebo, all blinded investigational product should be discontinued.

04T4BY Confidential

Protocol/Amendment No.: 002-01

4. Abnormal liver function tests meeting criteria specified below (see Section 12.5 for additional details on management and discontinuation of blinded investigational product for subjects with elevated liver enzymes).

- o ALT or AST  $\ge 3X$  ULN with total bilirubin (TBL)  $\ge 2X$  ULN and alkaline phosphatase (ALP) < 2X ULN and without an established etiology; or
- o ALT or AST ≥8X ULN or ≥3X ULN with symptoms consistent with liver injury and without an established etiology; or
- ALT or AST  $\geq$ 5X ULN for 2 weeks or longer; or

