## 7.1.2.13.2 Hypoglycemia

Based on review of the subject completed HAL at each clinic visit, the investigator must assess the glucose values as well as any symptoms of hypoglycemia reported by the subject. Events of hypoglycemia will be classified by the Sponsor according to the following categories (see Section 8.2.3.2).

Severe Hypoglycemia: An event requiring assistance of another person to actively administer carbohydrate, glucagon, or other resuscitative actions. These episodes may be associated with sufficient neuroglycopenia to induce seizure or coma. Fingerstick or plasma glucose measurements may not be available during such an event, but neurological recovery attributable to the restoration of plasma glucose to normal is considered sufficient evidence that the event was induced by a low plasma glucose concentration.

Documented Symptomatic Hypoglycemia: An event during which typical symptoms of hypoglycemia are accompanied by a measured fingerstick or plasma glucose concentration ≤70 mg/dL (3.9 mmol/L).

Asymptomatic Hypoglycemia: An event not accompanied by typical symptoms of hypoglycemia but with a measured fingerstick or plasma glucose concentration ≤70 mg/dL (3.9 mmol/L).

Probable Symptomatic Hypoglycemia: An event during which symptoms of hypoglycemia are not accompanied by a fingerstick or plasma glucose determination, but was presumably caused by a plasma glucose concentration ≤70 mg/dL (3.9 mmol/L). Since many people with diabetes choose to treat symptoms with oral carbohydrate without a test of plasma glucose, it is important to recognize these events as probable hypoglycemia.

**Protocol/Amendment No.:** 002-01

Relative Hypoglycemia: An event during which the person with diabetes reports any of the typical symptoms of hypoglycemia, and interprets the symptoms as indicative of hypoglycemia, but with a measured plasma glucose concentration >70 mg/dL (3.9 mmol/L). This classification reflects the fact that patients with chronically poor glycemic control can experience symptoms of hypoglycemia at plasma glucose levels >70 mg/dL (3.9 mmol/L) as plasma glucose concentrations decline toward that level.

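### Read literally, 7.1.3 does not release a single low central-laboratory FPG to the site, although the hypoglycemia stop criterion counts FPG and the HA eCRF rule covers every glucose value at or below 70 mg/dL

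*Combined protocol and SAP*

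**What the plan says.** **Masking and release (7.1.3).** "Glycemic measurements (e.g., FPG, A1C) and C-peptide measurements will be masked from Visit 4/Randomization (Day 1"). The exception is that the "central laboratory will report to the investigator in an unmasked manner if an FPG or A1C value meets criteria for glycemic rescue or discontinuation". The full condition, with its cross-reference, is "if an FPG or A1C value meets criteria for glycemic rescue or discontinuation from blinded investigational product criteria (see Sections 5.6 and 5.8"). A separate list of laboratory flags follows, covering creatinine, eGFR, liver tests and pregnancy. It has no glucose entry, high or low.

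**Stop criterion (5.8 item 3).** "Hypoglycemia: Repeated (2 or more episodes since the prior visit) FPG or fingerstick glucose", with two limbs: "<50 mg/dL (2.8 mmol/L) with or without symptoms of hypoglycemia, or" "≤70 mg/dL (3.9 mmol/L) with symptoms of hypoglycemia, and without a reasonable explanation". Section 7.1.2.12 says that central-laboratory FPG is used to assess discontinuation and refers to 5.8 without limiting this to high values.

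**Definition (7.1.2.13.2).** An event without typical symptoms is asymptomatic hypoglycemia if it comes "with a measured fingerstick or plasma glucose concentration ≤70 mg/dL (3.9 mmol/L"). Plasma values therefore count.

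**Recording rule (7.1.1.8.2 and 7.1.2.13.2.1).** The HA eCRF is mandatory for "all glucose values ≤70 mg/dL (3.9 mmol/L"), whether or not the investigator calls the episode an adverse event. No source of measurement is excluded.

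**Unmasked data.** Section 7.1.2.9 bases glimepiride titration on fingersticks. Section 7.1.2.10 bases titration and hypoglycemia discontinuation on home glucose readings (SMBG) and the Hypoglycemia Assessment Log (HAL).

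**The concern.** The release rule and the rules that depend on glucose values do not fit together at the low end. Item 3 counts FPG episodes, but an FPG episode can be added to fingerstick episodes only if someone sees both, and on a literal reading nobody at the site sees the FPG. The form rule makes no exception for a value the site is never shown.

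Two things are at stake.

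- **Safety oversight.** Table 5 (5.2.1.2.1) makes up-titration conditional on no hypoglycemic episode since the last increase. A masked FPG at or below 70 mg/dL is an episode by the protocol's own definition, yet the person deciding on titration may not know of it.
- **Summaries.** Under Analysis of Hypoglycemia (8.2.3.2), HA eCRF episodes that are not adverse events are summarized, and their number influences whether further Tier 3 summaries are made. Masked low values are missing from that count. Section 4.2.1 associates sulfonylureas with hypoglycemia, so the shortfall need not be equal across arms.

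**Working it through.** The plan gives no figure on this point to reproduce. The check is mainly a comparison of the rules, case by case.

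| Central FPG result | Meets 5.8 item 3 on what the laboratory knows? | Released under 7.1.3? | HA eCRF required? |
|---|---|---|---|
| Repeated values below 50 mg/dL between visits (for example a scheduled and an unscheduled draw) | Yes | Yes | Yes |
| A single value below 50 mg/dL | No: at least two episodes are needed | No | Yes |
| 50 to 70 mg/dL, no symptoms | No | No | Yes |
| At or below 70 mg/dL, subject had symptoms | Laboratory cannot tell: no stated access to symptoms | Undefined | Yes |

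The gap is in rows 2 to 4. The Trial Flow Chart (6.0) schedules one FPG per visit, so row 1 needs an unscheduled draw.

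**Comparison with other repeat-based criteria.** High FPG must be consistently above threshold, and the note in 5.8 defines consistency as a repeat within 7 days of laboratory notification, so the first value has to trigger a notice. Creatinine and eGFR must also be consistently abnormal, and 7.1.3 flags single values of both. Item 3 has neither a repeat-after-notification note nor a flag.

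**Number of draws.** FPG is scheduled at 10 post-baseline visits (Visits 5 to 14), with 410 subjects per arm.

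- Without attrition: 410 × 10 = 4,100 draws per arm.
- With the cumulative attrition of 8.2.6, the proportions remaining at Weeks 6 to 52 are 0.927, 0.909, 0.888, 0.840, 0.790 and 0.688, which sum to 5.042.
- Holding 0.688 for Weeks 65, 78, 91 and 104 (an assumption) adds 4 × 0.688 = 2.752.
- Total: 410 × (5.042 + 2.752) = 410 × 7.794 ≈ 3,196 draws per arm.

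**Same-visit clinic fingerstick.** The flow chart schedules one at Visits 5 to 13, but not at Visit 14, Rescue or Discontinuation. Visit 14 contributes 410 × 0.688 ≈ 282 draws, or 282 / 3,196 ≈ 9%. About 91% of the scheduled draws thus have an unmasked reading from the same visit.

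**Low values.** The documents give no rate of FPG at or below 70 mg/dL. Purely for illustration, an assumed 0.5% to 2% gives 3,196 × 0.005 ≈ 16 to 3,196 × 0.02 ≈ 64 values per arm, before removing those that a same-visit fingerstick also shows to be low.

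**The case against.** The strongest reply is that the protocol deliberately runs hypoglycemia management on fingersticks and masks FPG to protect the blind. Item 3 accepts FPG or fingerstick glucose, 7.1.2.10 names SMBG and the HAL as the basis for hypoglycemia discontinuation, and most masked draws have a clinic fingerstick beside them. The form rule in 7.1.1.8.2 sits in a note about what subjects log, so it may mean only values known to the site. Visit 14 and Discontinuation come at the end of treatment, and a Rescue visit follows a high-glucose criterion.

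Much of this stands, and it rules out several stronger readings that a reader might infer:

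- *That all low FPG stays masked.* The release sentence cites 5.8 as a whole, including item 3. A low FPG that met item 3 would be released.
- *That the missing low-glucose flag shows low values were overlooked.* The list has no high-glucose entry either, because FPG release is handled in the sentence before it.
- *That the stop and titration rules cannot be followed.* Both can be applied from unmasked fingerstick, SMBG and HAL data.
- *That the values are lost.* FPG is an analyzed efficacy endpoint (Table 10), so every central result is trial data.
- *That the confirmatory hypoglycemia comparison is biased.* The Tier 1 analysis counts symptomatic adverse events with or without a confirming glucose value.

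The reply does not remove the inconsistency. Section 7.1.2.12 brings central FPG into the discontinuation assessment, 7.1.2.13.2 counts plasma glucose, and 7.1.2.13.2.1 states the form rule without restriction. Nothing says how the laboratory is to apply a criterion that depends on repetition or on symptoms.

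**Conclusion.** The concern holds in a limited form. On a literal reading, a single low central FPG is not released, so it cannot be counted with fingerstick episodes under 5.8 item 3. An FPG at or below 70 mg/dL that meets no stop criterion stays masked although the HA eCRF rule, as written, covers it.

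The consequence is for safety oversight, for the summary of HA eCRF episodes not reported as adverse events, and for asymptomatic-episode counts. The Tier 2 count of any hypoglycemia adverse event is touched only where the investigator would have reported an asymptomatic value as an adverse event.

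The size cannot be derived from the documents. The 3,196 draws per arm rest on the plan's attrition rates and a flat continuation after Week 52. The 16 to 64 low values rest on an assumed rate and overstate what goes unseen, because same-visit fingersticks are not deducted. The conclusion also assumes that no laboratory manual or other document outside the protocol supplies a low-FPG alert.

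**What to change.** Reconcile 5.8 item 3, 7.1.1.8.2, 7.1.2.12, 7.1.2.13.2.1 and 7.1.3 on two questions:

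1. Does the central laboratory notify sites of low FPG under the existing criteria, and if so how, given that those criteria depend on repetition and, in one limb, on symptoms?
2. Does the HA eCRF rule cover masked central FPG, or only values known to the site?

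This asks for no new threshold and no change to the stop criterion. How the clinical rules should read is for the sponsor to decide.

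If such values stay masked, add to 8.2.3.2 a table by arm of central-laboratory FPG at or below 70 mg/dL, the limit already in 7.1.2.13.2. It would be drawn from the laboratory database and shown beside the HA eCRF summary.

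The cost is a short text amendment plus one small table or, if sites are notified, a laboratory alert. Notification would let sites see a few low values that could hint at the glimepiride arm, but sites already see fingerstick readings.

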# 7.1.3.1 Laboratory Evaluations (Hematology, Chemistry, Urinalysis and Others)

Laboratory tests for hematology, chemistry and urinalysis and others are specified in Table 7.

**Table 7 Laboratory Evaluations** 

Hematology	Chemistry	Urinalysis a	Others

 
Hemoglobin
 
Hematocrit
 
RBC Count
 
Platelet Count
 
WBC Count
 
Total Neutrophils (Abs)
 
Eosinophils (Abs)
 
Monocytes (Abs)
 
Basophils (Abs)
 
Lymphocytes (Abs)
 
	
 
BUN
 
Serum Creatinine (eGFR calculated using the MDRD formula)
 
Calcium (total)
 
Sodium
 
Potassium
 
Chloride
 
Total Carbon Dioxide (Bicarbonate)
 
Magnesium
 
Phosphate
 
Uric Acid
 
AST (SGOT)
 
ALT (SGPT)
 
Alkaline Phosphatase
 
Total Bilirubin
 
Direct (conjugated) Bilirubinb
 
Indirect (unconjugated) Bilirubinb
 
Albumin
 
Total Protein
 
	
 
pH
 
Protein (qual)
 
Blood (qual)
 
Ketones
 
Leukocyte Esterase
 
Nitrites
 
Microscopyc
 
	
 
TSH
 
Fasting C-peptide
 
A1C
 
FPG
 
Proinsulin
 
Urinary         Albumin/Creatinine         Ratioa
 
Pregnancy Tests         (where applicable)
 
Lipid Panel (i.e.,         Total Cholesterol,         HDL-C, non-HDL-C         LDL-C, and         Triglycerides)
 

<sup>a Samples should not be obtained if the subject is menstruating, has vigorously exercised within 24 hours, or had fever or an active infection within 2 days of the visit. Under such circumstances, the subject should provide a urine sample at an unscheduled visit.

Routine laboratory safety tests will be performed after at least a 10-hour fast (i.e., no food, double-blind investigational product, open-label AHA medication [metformin or sitagliptin (if applicable)], or drink except water and non-AHA non-investigational product as prescribed).

<sup>b Both direct and indirect bilirubin measured only when total bilirubin is greater than ULN.

<sup>c Microscopy performed if the central laboratory dipstick evaluation is positive for blood, nitrites, leukocytes and/or protein. Subjects found to have microscopic hematuria (defined as the presence of three or more red blood cells per high powered field on microscopic examination) from a properly collected, non-contaminated urinalysis with no evidence of infection should be referred to an urologist for appropriate work-up.

**Protocol/Amendment No.:** 002-01

#### 7.1.3.2 Future Biomedical Research

The following specimens are to be obtained as part of Future Biomedical Research:

- Blood for genomics use
- Plasma for future biomedical research
- Serum for future biomedical research

#### 7.1.4 Other Procedures

#### 7.1.4.1 Withdrawal/Discontinuation

Subjects who discontinue/withdraw from treatment prior to completion of the treatment regimen should be encouraged to continue to be followed for all remaining study visits.

When a subject discontinues/withdraws from participation in the trial, all applicable activities scheduled for the Discontinuation Visit should be performed at the time of discontinuation. Any adverse events which are present at the time of discontinuation/withdrawal should be followed in accordance with the safety requirements outlined in Section 7.2 - Assessing and Recording Adverse Events.

# 7.1.4.1.1 Withdrawal From Future Biomedical Research

Subjects may withdraw their consent for Future Biomedical Research and have their specimens and all derivatives destroyed. Subjects may withdraw consent at any time by contacting the principal investigator for the main trial. If medical records for the main trial are still available, the investigator will contact the Sponsor using the designated mailbox and a form will be provided by the Sponsor to obtain appropriate information to complete specimen withdrawal. Subsequently, the subject's specimens will be removed from the biorepository and be destroyed. A letter will be sent from the Sponsor to the investigator confirming the destruction. It is the responsibility of the investigator to inform the subject of completion of destruction. Any analyses in progress at the time of request for destruction or already performed prior to the request being received by the Sponsor will continue to be used as part of the overall research trial data and results. No new analyses would be generated after the request is received.

In the event that the medical records for the main trial are no longer available (e.g., if the investigator is no longer required by regulatory authorities to retain the main trial records) or the specimens have been completely anonymized, there will no longer be a link between the subject's personal information and their specimens. In this situation, the request for specimen destruction cannot be processed.

**Protocol/Amendment No.:** 002-01

#### 7.1.4.2 Blinding/Unblinding

IVRS/IWRS should be used for emergency unblinding in the event that this is required for subject safety. The emergency unblinding call center will provide after-hours emergency unblinding coverage when the investigator is not available.

In the event that unblinding has occurred, the circumstances around the unblinding (e.g., date and reason) must be documented promptly, and the Sponsor Clinical Monitor notified as soon as possible. Only the principal investigator or delegate and the respective subject's code should be unblinded. Trial site personnel and Sponsor personnel directly associated with the conduct of the trial should not be unblinded.

#### 7.1.5 Visit Requirements

Visit requirements are outlined in Section 6.0 - Trial Flow Chart. Specific procedure-related details are provided above in Section 7.1 - Trial Procedures.

